Study protocol

A Single-Center, Single-Arm, and Open-Label Clinical Study of Anti-PD-1 Antibody SHR-1210 in Combination with Apatinib Mesylate for the Treatment of Advanced Mucosal Malignant Melanoma

Protocol Number: SHR-1210-APT-N-MM

Compounds Name: Recombinant Humanized Anti-PD-1 Monoclonal Antibody for Injection (SHR-1210)

Apatinib Mesylate Tablets

Protocol Responsible Person:

Clinical Study Site:

Principal Investigator:

Sponsor:

Compound Sponsor: Jiangsu Hengrui Pharmaceutical Co., Ltd.

[name],

[name]

Protocol Synopsis

Title	A Single-Center, Single-Arm, and Open-Label Clinical Study of Anti-PD-1 Antibody SHR-1210 in Combination with Apatinib Mesylate for the Treatment of Advanced Mucosal Malignant Melanoma
Protocol Number	SHR-1210-APTN-MM
Study Duration	January 2019 ~ January 2022
Study Objectives	
Primary Objectives
 
To evaluate the objective response rate (ORR) of SHR-1210 in combination with apatinib mesylate in the treatment of patients with advanced mucosal melanoma
 
Secondary Objectives
 
 1. To observe and evaluate the progression-free survival (PFS), duration of response (DOR), time to response (TTR), disease control rate (DCR), overall survival (OS), and 6-month/9-month/12-month survival rates in patients with advanced mucosal melanoma treated with SHR-1210 in combination with apatinib mesylate 2. To evaluate the safety of SHR-1210 in combination with apatinib

	
mesylate in the treatment of patients with advanced mucosal melanoma
 
Exploratory Objectives
 
 1. To evaluate the predictive, prognostic, and pharmacodynamic exploratory biomarkers in archived and/or fresh tumor tissue and blood samples, and to assess the correlation between these biomarkers and disease progression 2. To evaluate the quality of life in patients with advanced mucosal melanoma treated with SHR-1210 in combination with apatinib mesylate
Study Endpoints	
Primary Study Endpoints
 
Assessed ORR per Response Evaluation Criteria in Solid Tumors (RECIST) 1.1 criteria
 
Secondary Study Endpoints
 
Efficacy:
 
Assessed PFS per RECIST 1.1 criteria
 
 * Time to response (TTR) * Duration of response (DOR) * Disease control rate (DCR) * 6-month survival rate * 9-month survival rate * 12-month survival rate * Overall survival (OS)

	
Safety
 
 * Incidence and severity of adverse events (AEs) and serious adverse events (SAEs), abnormal laboratory values, determined according to the National Cancer Institute (NCI) - Common Terminology Criteria for Adverse Events (CTCAE) V4.03criteria * Dose interruption rate, dose discontinuation rate due to AEs 
Exploratory Study Endpoints
 
 * To explore the relationship between programmed cell death ligand-1 (PD-L1) expression level, proportion of positive cells, and/or other biomarkers, such as tumor mutation burden (TMB) at baseline, and efficacy * To explore the correlation between biomarkers in archived and/or fresh tumor tissue and blood samples and disease progression * To evaluate the quality of life in patients with advanced mucosal melanoma treated with SHR-1210 in combination with apatinib mesylate

Study Subjects
	
 1. Patients with advanced mucosal malignant melanoma ineligible for radical surgery 2. Patients with advanced mucosal malignant melanoma experiencing recurrence and metastasis after radical surgery of the primary lesion

Study Design	
As a single-arm, open-label, and single-center clinical study, this study aims to observe and evaluate the efficacy and safety of anti-PD-1 (programmed cell death receptor-1) antibody SHR-1210 in combination with apatinib mesylate in patients with advanced mucosal melanoma.
 
The study subjects will be the patients with advanced mucosal melanoma who cannot be cured.
 
The study will enroll approximately 30 patients with advanced mucosal melanoma using ORR as the primary efficacy endpoint.
 
After obtaining informed consent and signing the informed consent form (ICF), the eligible subjects will continuously receive apatinib 500 mg, orally, once daily, and SHR-1210 200 mg, intravenously (IV), every 2 weeks. The dose of apatinib will be adjusted according to the patient's tolerance, with a treatment cycle of 4 weeks, until the treatment discontinuation events specified in the protocol occur. After the end of treatment, subjects will undergo post-treatment safety visits and survival follow-up. For subjects who discontinue treatment due to reasons other than disease progression or death, tumor progression follow-up will also be conducted after the end of treatment.
 
After the subjects are enrolled in the study, safety visits will be conducted before the administration of SHR-1210 on Day 1 and Day 15 of each treatment cycle. Imaging examinations will be performed every 2 cycles during the first 12 treatment cycles to evaluate the efficacy, and every 3 cycles thereafter until the end of treatment, withdrawal of informed consent, or death.
 
The study will also explore predictive, prognostic, and

--------------	--

	
pharmacodynamic exploratory biomarkers in archived and/or fresh tumor tissue and blood samples, and assess the correlation between these biomarkers and disease progression. For subjects who have signed the ICF for biomarker sample collection, biomarker blood samples and tumor samples will be collected at baseline period and during the study, including any potential tumor biopsies performed at baseline.

Study Drugs	
Recombinant Humanized Anti-PD-1 Monoclonal Antibody for Injection (Drug No. "SHR-1210") (Manufacturer: Suzhou Suncadia Biopharmaceuticals Co., Ltd.)
 
Apatinib Mesylate Tablets (Manufacturer: Jiangsu Hengrui Pharmaceutical Co., Ltd.)

Mode of Administration	
SHR-1210 will be administered via intravenous infusion (no prophylactic medication required) at a fixed dose of 200 mg, and 3 mg/kg for patients weighing < 50 kg at baseline. Each infusion will last for 30 minutes (no less than 20 minutes, no more than 60 minutes), and the drug will be administered once every 2 weeks, with 4 weeks for one cycle and the maximum cumulative treatment duration of 2 years.
 
Apatinib will be taken orally at a dose of 500 mg after a meal once daily. The dose of apatinib will be adjusted according to the patient's tolerance, with continuous administration and 4 weeks for one cycle.

Enrollment Criteria	
Patients must meet all the following inclusion criteria to be enrolled in this study:
 
 1. The patient voluntarily participates in the study and signs the ICF; 2. ≥ 18 years of age, male or female;

	
3. Clinically diagnosed or pathologically confirmed advanced mucosal malignant melanoma, with at least one measurable lesion that has not undergone local treatment (according to RECIST v1.1 requirements, the measurable lesion should have a long diameter of ≥ 10 mm or an enlarged lymph node should have a short diameter of ≥ 15 mm by a spiral computed tomography [CT] or magnetic resonance imaging [MRI] scan).4. Can swallow tablets normally;5. Eastern Cooperative Oncology Group (ECOG) score: 0 ~ 1;6. Expected survival ≥ 12 weeks;7. The function of vital organs must meet the following requirements (no use of any blood components, cell growth factors, or other corrective therapeutic drugs is allowed within 14 days prior to the first administration of the investigational drug):
● Absolute neutrophil count $\geq 1.5 \times 10^9$ /L;● Platelets $\geq 80 \times 10^9$ /L;● Hemoglobin ≥ 90 g/L;● Serum albumin ≥ 30 g/L;● Thyroid stimulating hormone (TSH) $\leq 1 \times$ upper limit of normal (ULN) (in case of abnormality, free triiodothyronine [FT3] and free thyroxine [FT4] levels should be evaluated simultaneously; if FT3 and FT4 levels are within the normal range, the subject can be included in the study);● Bilirubin $\leq 1.5 \times$ ULN (within 7 days prior to the first administration of the investigational drug);
--	---

	
 ● Alanine aminotransferase (ALT) and Aspartate aminotransferase (AST) $\leq 1.5 \times$ ULN (within 7 days prior to the first administration of the investigational drug); ● Serum creatinine $\leq 1.5 \times$ ULN; 
8. For female patients who are non-surgically sterilized or of childbearing potential, they are required to use a medically approved contraceptive method (such as an intrauterine device, contraceptive medication, or condom) during the study treatment period and within 3 months after the end of the study treatment. Non-surgically sterilized women of childbearing potential must have a negative serum or urine human chorionic gonadotrophin (HCG) test within 72 hours prior to study enrollment, and must be non-lactating. For male patients with female partners of childbearing potential, effective contraception should be used during the study period and within 3 months after the last administration of SHR-1210.

Exclusion Criteria	
Patients with any of the following conditions will be excluded from the study:
 
 1. Patients who have any active autoimmune diseases or a history of autoimmune diseases (including, but not limited to: autoimmune hepatitis, interstitial pneumonia, uveitis, enteritis, hepatitis, hypophysitis, vasculitis, nephritis, hyperthyroidism, vitiligo, asthma (patients with asthma that has completely resolved in childhood requires no any medical intervention in adulthood can

	
be included; patients with asthma requiring medical intervention with bronchodilators cannot be included);
 
2. Patients who are receiving immunosuppressive agents or systemic hormonal therapy for immunosuppression (at doses > 10 mg/day prednisone or other equivalent hormonal therapy) and are still on treatment within 2 weeks prior to enrollment;3. Severe allergic reactions to other monoclonal antibodies;4. Patients with hypertension that cannot be well controlled with antihypertensives (systolic blood pressure \geq 140 mmHg or diastolic blood pressure \geq 90 mmHg);5. Uncontrolled clinical symptoms or disease of the heart, such as:
● New York Heart Association (NYHA) grade 2 or higher heart failure● Unstable angina● Myocardial infarction within 1 year● Clinically significant supraventricular or ventricular arrhythmias requiring treatment or intervention● QTc > 450 ms (male); QTc > 470 ms (female);6. Abnormal coagulation function (international normalized ratio [INR] > 2.0, prothrombin time [PT] > 16 s), with a bleeding tendency or currently receiving thrombolytic or anticoagulant therapy (the prophylactic use of low-dose aspirin and low molecular weight heparin is allowed);7. Within 3 months prior to enrollment, subjects with significant clinically relevant bleeding symptoms or a clear bleeding
--	--

	
tendency, such as hemoptysis (≥ 2.5 mL/day), gastrointestinal bleeding, esophageal and gastric varices with a risk of bleeding, hemorrhagic gastric ulcers, or vasculitis;
 
8. Arterial/venous thrombotic events within 6 months prior to enrollment, such as cerebrovascular accidents (including transient ischemic attacks, hemorrhage brain, cerebral infarction), deep vein thrombosis, and pulmonary embolism;
 
9. Known inherited or acquired bleeding and thrombophilia (such as hemophilia, coagulation disorders, and platelets decreased);
 
10. Urine protein $\geq ++$ indicated by urinalysis and confirmed 24-hour urine protein amount > 1.0 g;
 
11. Patients who have previously received radiotherapy, chemotherapy, hormonal therapy, or surgery and have not completed the treatment (last administration) 4 weeks prior to the initiation of the investigational drug; patients who have received molecular targeted therapy (including other oral targeted drugs in clinical studies) within less than 5 drug half-lives prior to the first administration of the investigational drug, or patients whose AEs (except alopecia) caused by previous treatments have not recovered to \leq CTCAE grade 1;
 
12. Patients with active infections, unexplained fever $\geq 38.5^{\circ}\text{C}$ within 7 days prior to medication, or baseline white blood cell count $> 15 \times 10^9/\text{L}$; or those with purulent and chronic infections, and prolonged wound healing;
 
13. Patients with bone metastases who have received palliative

--	---

	
radiotherapy to an area > 5% of the bone marrow area within 4 weeks prior to participating in this study;
 
14. Patients who have previously received anti-PD-1, anti-PD-L1, anti-PD-L2 therapy, or apatinib treatment;15. Known allergy to recombinant humanized anti-PD-1 monoclonal antibody drugs or their components;16. Patients with cutaneous melanoma, ocular melanoma, and melanoma of unknown primary origin;17. Patients with severe local invasion of the primary lesion in mucosal malignant melanoma, and with a risk of organ leakage, major bleed, or perforation;18. Pregnant or lactating women, or female patients of childbearing potential who have not taken contraceptive measures;19. Patients with other malignant tumors at the same time;20. Patients who participate in another clinical study at the same time;21. Patients with positive human immunodeficiency virus (HIV) or hepatitis C virus (HCV); Individuals who are positive for HBsAg or HBcAb and have detectable hepatitis B virus (HBV) DNA copies (quantitative detection limit is 500 IU/mL);22. Patients who have received live vaccine within 4 weeks prior to the initiation of treatment;23. Other severe, acute, or chronic medical or mental diseases or laboratory abnormalities that may increase the risk associated with study participation or may interfere with the interpretation of
--	--

	study results as judged by the investigators.
Discontinuation Criteria	
 1. The subject withdraws informed consent and requests withdrawal; 2. For patients identified with progressive disease by imaging: 
 ● According to the RECIST v1.1 criteria, if disease progression is observed for the first time, confirmation is required 4 ~ 6 weeks later (except for rapid progression and significant clinical progression); ● Upon confirmation of disease progression in the subject, if the clinical symptoms are stable, the investigator may decide to continue treatment until further radiographic progression is observed; ● Stable clinical symptoms are defined as the following: 
 a. No significant clinical symptoms or changes in laboratory test indicators; b. No change in performance status score (no worsening); c. Rapid progression of non-tumor and tumor progression not involving vital organs/sites (such as spinal cord compression); 3. When the cumulative usage of SHR-1210 reaches 2 years (without radiographic progression) and the radiographic examination confirms a complete response (CR), the medication may be considered for discontinuation after completing 12 treatment cycles;

	
 4. Intolerant of toxicity; 5. Poor subject compliance; 6. The subject is lost to follow-up or becomes pregnant; 7. Other circumstances that, in the opinion of the investigator, a withdrawal from the study is necessary.
Study Discontinuation Criteria	
Discontinuation criteria for this study include, but are not limited to, the following:
 
 1. Identify unexpected, significant, or unacceptable risks to patients; 2. Major errors in the protocol are found during the implementation of the study; 3. Investigational drug/therapy is ineffective, or continuing the study is meaningless; 4. The sponsor decides to terminate the study due to reasons such as severe delay in patient enrollment or frequent protocol deviations.
Safety Evaluation	
The severity of AEs will be assessed according to the CTCAE v4.0.3 criteria. During the trial, the adverse event record form should be filled out truthfully, including the onset time, severity, causality with the study drug, duration, actions taken, and outcome of the AE.

Concomitant Medications and Therapies	
During the study, the investigator is allowed to provide appropriate supportive therapy based on the clinical needs of subjects. the following Specific medications can be found in the following description of concomitant medications. The use of anti-tumor treatments not specified in the study protocol is prohibited during the treatment, except

	
for medical interventions taken for life-threatening tumor emergencies.
 
1. Permitted concomitant medications
● All concomitant medications/treatments must be recorded in the case report form (CRF), including all prescriptions, over-the-counter drugs, traditional Chinese herbal medicines, intravenous medications, and fluids.● If changes occur during the study, the drug dose, frequency, mode and date of administration should also be recorded in the CRF.2. All concomitant medications/treatments must be recorded between 30 days before the first administration of the investigational drug and 30 days after the last administration in the study.3. Prohibited concomitant medications 
During the screening and treatment periods of the study, subjects are prohibited from receiving the following treatments:
 
● Systemic anti-tumor chemotherapy or biotherapy● Immunotherapy not specified in this protocol● Investigational drugs other than SHR-1210 and apatinib mesylate tablets● Vaccination within 4 weeks prior to treatment administration and during the administration period. Examples of vaccines include, but are not limited to: measles, mumps, rubella, varicella, yellow fever, rabies, Bacillus of Calmette and Guérin, and typhoid (oral) vaccines.
--	---

	
 ● Use of any glucocorticoids other than the treatment of AEs caused by immunotherapy and anti-angiogenic therapy (Note: The physiological doses of steroids may be permitted after communication with the sponsor).
--	---

Study Visits	
 ● Screening / Baseline Period (Day -21 to Day 0) 
Only after the subject signs the ICF approved by the Institutional Review Board (IRB), the screening and tumor assessment related to the clinical study can be initiated. During the screening period, the following tests will be performed: complete medical history, physical examination, height, weight, vital signs (blood pressure and heart rate), electrocardiogram (ECG), ECOG score, etc. Past medications and clinical laboratory tests, including urinalysis, hematology (differential blood count), blood chemistry, coagulation function, stool routine, myocardial zymogram, and lymphocyte subsets must be performed within one week before drug administration. Thyroid function, pituitary-adrenal axis function, virological parameters, and pregnancy test (only for women of childbearing potential) must be completed within 21 days before the first drug administration. Tumor assessment must be completed within 3 weeks before the administration of the study drug (additional nasopharyngeal MRI or CT for nasopharyngeal melanoma, additional oropharyngeal MRI or CT for oropharyngeal melanoma, colposcopy for female genital tract

--------------	--

	
melanoma as needed, and colonoscopy for rectal melanoma as needed). Concurrently, pathological tissue and blood samples will be collected for pathological consultation and genetic testing.
 
● Treatment Period 
The subjects will receive recombinant humanized anti-PD-1 monoclonal antibody injection in combination with apatinib according to the protocol. Treatment may be terminated in the event of recurrent disease metastases, intolerable toxicity, withdrawal of informed consent, or other criteria for treatment withdrawal.
 
At each visit, the concomitant medications and clinical symptom information of the subjects will be recorded, including any AEs. All subjects will undergo imaging assessments every 2 cycles during the first 12 treatment cycles, and every 3 cycles thereafter until the end of treatment, withdrawal of informed consent, or death. Cranial CT or MRI and bone scans will be performed annually (increase the frequency of imaging assessments if clinically indicated) until the end of the study.
 
● Visits After the End of Study Treatment: 
After the termination of the study treatment, the subjects should undergo the following safety evaluations: physical examination, vital signs, ECOG, ECG, hematology, urinalysis, stool routine, blood chemistry, coagulation function, thyroid function, lymphocyte subsets, and pregnancy test (only for women of childbearing potential). The date and reason for termination of the

--	--

	
study treatment must be clearly recorded in the CRF for the termination of the study treatment.
 
All subjects who complete the study treatment or withdraw from the study will be followed up for safety through outpatient visits or telephone follow-ups within 90 days after the last administration of the investigational drug, or until the patient receives another anti-tumor treatment, whichever occurs first.

Statistical Analysis	
The main results of this study will be presented using descriptive statistical methods. The mean, standard deviation, median, maximum, and minimum values will be listed for measurement data, while the frequency (proportion), rate, and confidence interval (CI) will be listed for counting data and ranking data. All statistical analyses will be programmed and calculated using SAS 9.4 or above.
 
 ● Safety Analysis: 
The descriptive statistical analysis will be used for analyzing AEs, SAEs, and adverse reactions (adverse reactions are defined as AEs with the causality to the study drug as "definitely related/possibly related/not evaluable") occurring in various populations. The worst clinical grade will be described for the laboratory test results at baseline and post-baseline.
 
 ● Efficacy Analysis: 
The point estimates will be performed for efficacy endpoints such as ORR and DCR, and their 95% CIs will be provided. The interval estimates will be performed using the Clopper-Pearson

	
method.
 
PFS, DOR, OS, 6-month, 9-month and 12-month survival rates will be estimated using the Kaplan-Meier method, and 95% CIs will be calculated. TTR will be described using mean, standard deviation, median, maximum, and minimum values.
 
● Additional Analyses: 
For the SHR-1210-related solid tumor biomarkers, such as PD-L1 or other biological markers levels in tumor tissues, descriptive statistics will be used for analysis.

--	--

List of Abbreviations and Related Terms

Acronyms / Abbreviations	Explanation
ADA	Anti-drug antibody
ADR	Adverse drug reaction
AE	Adverse events
ALP	Alkaline phosphatase
ALT (SGPT)	Alanine aminotransferase
APTT	Activated partial thromboplastin time
AST (SGOT)	Aspartate aminotransferase
ANC	Absolute neutrophil count
AUC	Area under the concentration-time curve
BUN	Blood urea nitrogen
CBC	Complete blood count
Cl ⁻	Chlorine
CRP	C-reactive protein
CT	Computer-assisted tomography
CTCAE	Common Terminology Criteria for Adverse Events
DLT	Dose limiting toxicity
DSMB	Data and Safety Monitoring Board
EC	Ethics Committee
ECG	Electrocardiogram
ECOG	Eastern Cooperative Oncology Group

CRF	Case report form
EDC	Electronic data capture
FAS	Full analysis set
CFDA	China Food and Drug Administration
GCP	Good Clinical Practice
GLP	Good Laboratory Practice

HIV	Human immunodeficiency virus
IC	Informed consent
ICF	Informed consent form
ICH	International Coordinating Organization
INR	International normalization ratio
IRB	Institutional Review Board
IV	Intravenous
K ⁺	Potassium
K _d	Dissociation constant
kg	Kilogram
LDH	Lactate dehydrogenase
Mab	Monoclonal antibody
MedDRA	Medical Dictionary for Registration Projects
mg	Milligram
mL	Milliliter
MRI	Magnetic resonance imaging
MTD	Maximum tolerated dose
Na ⁺	Sodium
NK	Natural killer
PBMC	Peripheral blood mononuclear cells
PBSCT	Peripheral blood stem cell transplantation
PD	Progressive disease

PK	Pharmacokinetics
PS	Performance status
PT	Prothrombin time
PLT	Platelets
RBC	Red blood cells
RECIST	Response Evaluation Criteria in Solid Tumors
RO	Receptor occupancy
SAE	Serious adverse event
SAP	Statistical analysis plan
SOP	Standard operating procedure
$t_{1/2}$	Half-life
TCR	Tissue cross-reactivity
WBC	White blood cells

Protocol Text

1. Study Background

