5.2. Dosing regimen

SHR-1210 will be administered via intravenous infusion (no prophylactic medication required) at a fixed dose of 200 mg, and 3 mg/kg for patients weighing < 50 kg at baseline. Each infusion will last for 30 minutes (no less than 20 minutes, no more than 60 minutes), and the drug will be administered once every 2 weeks, with 4 weeks for one cycle and the maximum cumulative treatment duration of 2 years.

During the study period, SHR-1210 will be administered once every 2 weeks, with a dosing window of ±3 days from the scheduled dosing time. If the administration of SHR-1210 is delayed by more than 3 days from the scheduled dosing time, the dose will not be given for that time, and the original dose will be given at the next scheduled dosing time.

Apatinib will be taken orally after a meal, once daily, with 2 tablets per dose (250 mg per tablet). The dose of apatinib will be adjusted according to the patient's tolerance, with continuous administration and 4 weeks for one cycle.

Definition of "Administration after a meal": Administration within 30 minutes of the end of meal.

Patients will receive the investigational drug until the treatment discontinuation criteria specified in the protocol are met.

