5.3. Dose modifications

During the study period, dose modifications of the investigational drug can be made based on its toxic side effects, including: dose interruption, dose reduction, modification of administration mode, and dose termination.

Dose interruption is allowed for SHR-1210, with a maximum allowable drug interruption of 12 weeks.

In addition to dose interruption, for subjects whose weight decreases to below 50 kg during the treatment period, the dose of SHR-1210 may be down-titrated to 3 mg/kg q2w, as appropriate.

Dose modifications due to apatinib-related toxicity include: dose interruption, dose reduction, modification of administration mode (first modification: 5 days on treatment and 2 days off; second modification: 7 days on treatment and 7 days off), and dose termination. During the study, after adjusting the administration mode of apatinib, the recovery of dose mode will not be allowed.

During the study, if definite apatinib-related AEs occur, such as hypertension, proteinuria, hand and foot syndrome (HFS), apatinib administration may be down-titrated or interrupted. After toxicity recovery, the original dose, adjusting the administration method, or terminating the dose may be given as appropriate. After discontinuing apatinib, the study subjects may continue to receive SHR-1210 monotherapy.

During the study, if immune-related toxicities occur, such as immune pneumonia,

hepatitis, enteritis, the administration of SHR-1210 and apatinib should be suspended as appropriate. Once the toxicity has recovered to \leq grade 1 or baseline levels (for the increase of laboratory parameters such as ALT/AST and total bilirubin [TBIL]), the medication can be resumed. The administration of SHR-1210 should be resumed first, and after 14 days of observation without significant abnormalities, the administration of apatinib can be initiated and the mode of subsequent administration of apatinib will be adjusted.

During the study, if \geq grade 3 immune pneumonia, \geq grade 3 TBIL increased, grade 4 ALT/AST increased, or other grade 4 immune-related toxic reactions, grade 4 injection reactions occur, or if the immune-related toxicity causes a temporary suspension of SHR-1210 administration for more than 12 weeks and still cannot recover to \leq grade 1 or baseline level, SHR-1210 must be permanently discontinued.

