During the study, if \geq grade 3 capillary hyperplasia occurs, no dose modifications are required for apatinib, and SHR-1210 should be suspended until the toxicity recovers to \leq grade 2.

During the study, if the subject exhibits abnormal symptoms/signs or laboratory indicators, symptomatic treatment should be taken promptly, and it is recommended to refer to the following table for corresponding dose modifications:

Table 1 Dose Modifications

Drug-related Toxicity		Grading	Dose Interrupted or Not		Criteria for Resumption of Dosing	Dose Modification Methods for Apatinib	Discontinuation Criteria
			SHR-1210	Apatinib			
SHR-1210 and apatinib-related toxicities	Hematologic toxicity	Grade 1 and 2	No	No	-	-	-
		Grade 3	Yes	Yes	When toxicity recovers to \leq grade 2	Original dose	After two modifications, if \geq grade 3 hematologic toxicity occurs again, the administration of apatinib will be terminated.
	Grade 4	Yes	Yes	When toxicity recovers to \leq grade 2	First modification: Adjust to 5 days on treatment and 2 days off; Second modification: Adjust to 7 days on treatment and 7 days off;		
	Immune-related	Grade 2	Yes	No	When toxicity recovers	First modification: Resume	Unable to recover to \leq grade

Drug-related Toxicity	Grading	Dose Interrupted or Not		Criteria for Resumption of Dosing	Dose Modification Methods for Apatinib	Discontinuation Criteria
		SHR-1210	Apatinib			
ated pneumonia				to ≤ grade 1	at original dose Second modification: Adjust to 5 days on treatment and 2 days off; Third modification: Adjust to 7 days on treatment and 7 days off	1 after > 12 weeks of discontinuation
ALT/AST and TBIL increased (after receiving	Grade 2 ALT or AST increased Grade 2 bilirubin	Yes	Yes	When toxicity returns to baseline	First modification: Adjust to 5 days on treatment and 2 days off; Second modification: Adjust to 7 days of on treatment	1. If discontinuation of the drug for >12 weeks still does not result in recovery to baseline levels, then terminate the use of

Drug-related Toxicity	Grading	Dose Interrupted or Not		Criteria for Resumption of Dosing	Dose Modification Methods for Apatinib	Discontinuation Criteria
		SHR-1210	Apatinib			
hepatoprotective treatment)	increased				and 7 days off;	SHR-1210.

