During the study, the investigator may make appropriate dose modifications in accordance with the above-mentioned dose modifications, taking into account the occurrence of drug-related toxicities in the subjects. For example, if a subject experiences multiple grade 2 drug-related toxicities and has poor tolerance to the study drug, the investigator may adjust the administration mode or reduce the dose of apatinib after temporarily discontinuing the drug and the toxicities have resolved.

During the study, if a subject experiences fever (> 38°C, requiring corrective treatment), or significant symptoms of gasping, polypnoea, breathlessness, the administration of SHR-1210 will not be given at the current or next scheduled dose time until the symptoms have resolved. After the symptoms have relieved and stabilized for more than 7 days, the administration of SHR-1210 will be resumed according to the subsequent planned schedule. If necessary, pneumonia should be ruled out by imaging examination before administration.

During the study period, if any of the following occurs: hypertensive crisis, hemorrhage brain, \geq grade 2 pulmonary hemorrhage, \geq grade 3 other hemorrhages, arterial thrombosis, grade 4 venous thrombosis, leukoencephalopathy syndrome, or gastrointestinal perforation, the administration of apatinib should be terminated, and the administration of SHR-1210 should be suspended. Active symptomatic treatment

should be provided, and the decision to continue SHR-1210 treatment will be based on the recovery status of the toxicity in the subject.

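### Criterion 8 counts men's 3 months of contraception from the last SHR-1210 dose, although apatinib can be the later study drug to stop

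*Protocol*

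**What the plan says.** Criterion 8 appears with the same wording in the Protocol Synopsis (Enrollment Criteria) and in Section 4.1. Women must use contraception "during the study treatment period and within 3 months after the end of the study treatment". For men with partners of childbearing potential, "effective contraception should be used during the study period and within 3 months after the last administration of SHR-1210".

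The study treatment is two drugs. Section 5.2 has apatinib taken once daily without a break; for the antibody it says "During the study period, SHR-1210 will be administered once every 2 weeks". The rules that bear on which drug stops last are:

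- Section 5.2, late infusions: "If the administration of SHR-1210 is delayed by more than 3 days from the scheduled dosing time, the dose will not be given".
- Section 5.3, length of a hold: "Dose interruption is allowed for SHR-1210, with a maximum allowable drug interruption of 12 weeks".
- Section 5.3, capillary hyperplasia of grade 3 or higher: "no dose modifications are required for apatinib, and SHR-1210 should be suspended until the toxicity recovers to" grade 2 or lower.
- Section 5.3, fever or marked breathlessness: "the administration of SHR-1210 will not be given at the current or next scheduled dose time until the symptoms have resolved".
- Section 5.3, immune-related toxicity: "the administration of SHR-1210 and apatinib should be suspended as appropriate". For grade 2 immune-related pneumonia, however, Table 1 interrupts SHR-1210 and not apatinib.

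Section 4.5 also lets patients who still benefit go on taking the investigational drug after the study is complete.

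**The concern.** One criterion uses two anchors for the same regimen. The women's anchor covers both drugs; the men's covers SHR-1210 only, and the protocol gives no reason for the difference. If SHR-1210 alone determined how long cover is needed, the women's clause would be expected to use that anchor too.

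The mismatch has an effect only if apatinib can be the later drug to stop. If it can, a man who obeys the text to the letter is protected for less time after his last study-drug dose than a woman on the same treatment. What is at stake is partner exposure and pregnancy, which the protocol takes seriously: pregnancy is a discontinuation criterion in Section 4.3.1 and an example of a significant medical event in Section 8.2.1. No efficacy estimate is affected.

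**Working it through.** **Can apatinib be the later drug?** Yes, by three routes.

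1. *Ordinary end of treatment.* Apatinib is daily and SHR-1210 is 2-weekly (Section 5.2). If treatment stops between infusions, the last apatinib tablet can come up to 14 days after the last infusion. No unusual toxicity is needed.
2. *A missed infusion.* An infusion more than 3 days late is skipped (Section 5.2), and SHR-1210 is withheld for fever or breathlessness (Section 5.3). Neither rule mentions apatinib. One skipped infusion allows a gap of up to 28 days.
3. *A hold on SHR-1210 alone.* For capillary hyperplasia of grade 3 or higher, apatinib is left unchanged (Section 5.3 and Table 1), and an SHR-1210 interruption may last 12 weeks. Table 1 shows the same split for grade 2 immune-related pneumonia, although the text of Section 5.3 points to suspending both drugs.

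**Formula.** Let *d* be the time from the last SHR-1210 dose to the last apatinib dose, and read *study period* as time on treatment. Then:

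- men's cover after the last apatinib dose = max(0, 3 − *d*) months
- women's cover = 3 months
- shortfall = min(3, *d*) months

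One month is taken as 30.44 days, so 3 months = 3 × 30.44 = 91.3 days.

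| Case | *d* (days) | Shortfall | Men's cover after last apatinib dose | Women's cover |
|---|---|---|---|---|
| Both drugs stop on the same day | 0 | 0 | 91.3 days = 3 months | 3 months |
| Treatment ends between infusions | up to 14 | up to 14/30.44 = 0.46 month | at least 91.3 − 14 = 77.3 days = 2.54 months | 3 months |
| One SHR-1210 dose skipped | up to 28 | up to 28/30.44 = 0.92 month | at least 91.3 − 28 = 63.3 days = 2.08 months | 3 months |
| Treatment ends at the close of a 12-week SHR-1210 hold, apatinib continued | 84 | 84/30.44 = 2.76 months | 91.3 − 84 = 7.3 days = 0.24 month | 3 months |

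The last row assumes that the 12 weeks run from the last SHR-1210 dose. Larger gaps would need long-term apatinib alone. The protocol does not expressly allow that, so no such case is counted.

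**What does *study period* mean?** The term is not defined. Section 6.2 uses it as the heading for the on-treatment visits, separate from end of treatment (6.3) and follow-up (6.4), and Section 5.2 uses it for the time in which SHR-1210 is dosed. Both fit the narrow reading used above. Section 5.5, on recording concomitant therapy, can be read more broadly. If follow-up is included, the shortfall can be 0.

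**The case against.** The strongest objection is that men must use contraception during the *study period* as well as for 3 months after SHR-1210, while the women's sentence uses the narrower *study treatment period*. Different words in neighbouring sentences may be meant to differ. The design includes post-treatment visits and survival follow-up, so on a broad reading men could be covered for longer than women. This stands as a limit on the size of the shortfall, which is conditional on the narrow reading. It does not remove the problem. Sections 5.2 and 6.2 favour the narrow reading, and for drug taken after study completion under Section 4.5 even a broad study period is over, leaving only the SHR-1210 anchor.

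Second, most dose rules do not make apatinib the later drug. Table 1 holds both drugs for hematologic, liver and other non-hematologic toxicity, and apatinib alone for grade 3 hypertension, proteinuria, hand and foot syndrome and headache. After immune toxicity SHR-1210 restarts first. The only single-drug continuation stated is SHR-1210 alone, and Section 6.3 ends treatment once the criteria of 4.3.1 are met. All of this is correct, and it makes the 84-day case rare: it needs a hold on SHR-1210 alone, used in full, with no restart and with apatinib taken throughout. The 14-day case needs none of that.

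Third, the protocol has no data on how long cover is needed after apatinib, so neither 2.54 months nor 0.24 month can be shown to be too short. That also stands. The claim is that the rule for men falls below the protocol's own standard for women, without explanation; harm is not demonstrated.

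**Conclusion.** The concern holds as a minor point. The two anchors differ, nothing else in the protocol ties a man's period to apatinib, and the dosing rules allow apatinib to be the later drug. The likely shortfall is small: up to 0.46 month at an ordinary end of treatment and up to 0.92 month after one skipped infusion. It reaches 2.76 months only in the 12-week case.

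These figures assume that *study period* means time on treatment; on a broader reading the shortfall can be nil. The number of men affected cannot be derived from the protocol. The design, the sample size and the ORR analysis are unaffected.

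**What to change.** In criterion 8 of the Protocol Synopsis and of Section 4.1, run the male period from *the last dose of either study drug, whichever is later*. Men then have at least 3 months of cover after the last study-drug dose in every case above, as women do, however *study period* is read. The sponsor should confirm that 3 months is the right length for both drugs and check that the consent form, which is not among the documents at hand, agrees.

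The cost is one phrase in two places plus the consent-form check.
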